##### **6.8.3.1. Procedural Angiography**

- Per Pass angiogram(s)
  - Obtained immediately after completion of each and every Envi™-SR, Control Device, and/or additional therapy pass
- Post-assigned device use angiogram
  - After the final assigned device use
- Post-procedure angiogram after all treatments (if different than post-assigned device use angiogram)
  - The final post procedure angiogram should comprise a full A-P lateral image.

#### **6.8.4. 24 Hour (-8/+12 hrs.) Follow-up**

The 24 hour (-8/+12) hour follow-up visit includes:

- An NIHSS examination, assessed by blinded and certified study team member
- CT or MRI imaging.
- Record any adverse events which occur after the procedure and up to the time of the 24-hour examination.

CT or MRI will be obtained to assess any presence of hemorrhage. It is preferred, but not required, that whether CT or MRI is taken at baseline, to make direct comparison easier, the same imaging modality is obtained at follow-up.

This visit is not applicable for enrolled screen failure subjects.

#### **6.8.5. 7 Day (-2/+3 days) or discharge Follow-up**

The 7 days (-2/+3 days) or discharge (whichever is sooner) follow-up visit includes:

- An NIHSS examination, assessed by blinded and certified study team member
- Abbreviated Physical Examination
- Concomitant medications
- Record any adverse events which occur after the 24-hour time point and up to the time of the 7 days (-2/+3 days) or discharge.

#### **6.8.6. 30 Day (±14 days) Follow-up**

The 30 days (±14 days) follow-up visit includes:

- A mRS per the RFA-A
- Abbreviated Physical Examination
- Concomitant medications
- Record any adverse events which occur after the 7 days (-2/+3 days) or discharge.

In-person assessment is preferred, however telemedicine assessment is acceptable if clinical visit not possible.

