### 3.6. Blinding

Each participating clinical site will have two (2) teams: an **unblinded team**, consisting of treating physicians and study coordinator who care for the patient/patient up to hospital discharge and clinical follow up visits, and a **blinded team**, with members certified in mRS assessment. The blinded team performs the mRS assessment at the 90-day visit, and the NIHSS assessment at the 24-hour and 7-day/discharge visits.

The Investigator will be blinded to treatment arm during screening, consent and enrollment, until point of randomization. At the point of randomization, the Investigator will be informed of which device is to be used in the procedure in order to safely perform the procedure according to the device IFU.

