### 3.6.3. Blinded Assessments

The following are blinded assessments:

- NIHSS at 24 (-8/+12) hours
- NIHSS at seven (7) days (-2/+3 days) or discharge
- mRS at 90 days ( $\pm$  15 days)

Imaging will be assessed by an independent Core Lab. The Core Lab reader will be blinded to the site assessments and clinical information during evaluation of the angiographic recanalization endpoints and intracranial hemorrhage.

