#### **6.8.7. 90 Day (±15 days) Follow-up**

The 90 Day (±15 days) follow-up visit includes:

- A mRS, assessed by blinded and certified study team member per the RFA-A
- Record any adverse events which occur after the 30 days (±14 days) or discharge time point and up to the time of the 90-day (±15 days) examination.

In-person assessment is preferred, however telemedicine assessment is acceptable if clinical visit not possible.

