#### **6.8.8. Unscheduled Visit Follow-up**

The unscheduled visit includes:

- mRS, assessed by blinded and certified study team member per the RFA-A (if possible)
- Concomitant medications
- Record any adverse events which occur since last study visit and up to the time of the 90-day examination.

In-person assessment is preferred, however telemedicine assessment is acceptable if clinical visit not possible.

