### 8.2.2. Missing and Censored Data

Missing data, which in this instance is defined as data that was not entered into the EDC system for analysis, may have an impact upon the interpretation of the trial data.

The primary presentation of the results for the primary and secondary endpoints using the ITT population will be based on the observed data with multiple imputation for missing endpoint data using SAS PROC MI. This procedure uses an iterative modeling approach to generate estimates for patients who withdraw prematurely, or the data is just not recorded, incorporating

multivariate imputation by fully conditional specification (FCS) methods. The discriminant function method will be used for classification variables. With the function method of classification, the missing values will be imputed sequentially in the following order:

- Age: ( $\geq 67$  and  $< 67$ )
- Site of occlusion: ICA, MCA M1, MCA M2
- Baseline/Enrollment NIHSS score ( $< 17$  and  $\geq 17$ )
- Prior IV t-PA usage (Yes / No)
- Time to symptom onset ( $\geq 6$  hours and  $< 6$  hours)
- Baseline ASPECTS (6-7 and 8-10)

Each missing score will be imputed ten times to generate ten imputed complete datasets based on the Markov Chain Monte Carlo (MCMC) method with age, occlusion site, NIHSS score ( $< 17$  /  $\geq 17$ ), baseline ASPECTS (6-7 / 8-10), prior IV t-PA usage (yes / no), and time to symptom onset ( $\geq 4$  hours /  $< 4$  hours) entered into the model following this sequential order. The imputed score will be rounded to the first decimal point for continuous variables. Proc MIANALYZE will be used to combine the imputed datasets to render an analysis of the binary outcomes for the results for the primary effectiveness and safety endpoints and the applicable 4 secondary endpoints. The relevant secondary endpoint analysis will follow the method outlined to calculate the odds ratio with the imputed dataset.

Additional sensitivity analyses will also be conducted as a secondary examination of the primary analysis using the last observation recorded following the procedure observation carried forward. A tipping point analysis will also be conducted.

If a patient did not have solicited adverse events of special interest [incidence by type of event] prior to withdrawing prematurely from the study, the patient will be considered as not having experienced the event.

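### The 30-day mRS is not assigned to the blinded assessor, although the last-observation-carried-forward sensitivity analysis can use it in place of a missing 90-day score

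*Combined protocol and SAP*

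**What the plan says.** The plan schedules two mRS assessments after the procedure, at day 30 and day 90, and allows one at unscheduled visits.

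- **Day 90.** Section 6.8.7 asks for "A mRS, assessed by blinded and certified study team member per the RFA-A". The schedule of events (6.8.10) marks this score with footnote 8, which requires a blinded and certified assessor. Section 3.1 makes blinded assessment part of the definition of the primary endpoint.
- **Day 30.** Section 6.8.6 asks for "A mRS per the RFA-A". It names no assessor, and the schedule cell has no footnote.
- **Unscheduled visits.** Section 6.8.8 asks for a blinded and certified assessor if possible. The schedule cell again has no footnote.

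Section 3.6 defines the blinded team's work: "The blinded team performs the mRS assessment at the 90-day visit, and the NIHSS assessment at the 24-hour and 7-day/discharge visits". It describes the unblinded team as "consisting of treating physicians and study coordinator who care for the patient/patient up to hospital discharge and clinical follow up visits". Section 3.6.3, under "The following are blinded assessments", lists the 24-hour NIHSS, the 7-day or discharge NIHSS and the 90-day mRS. The blinded assessor's role in Section 6.4 covers the 90-day evaluation.

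On missing data, Section 8.2.2 makes multiple imputation the primary method and adds sensitivity analyses of the primary analysis, one of them "using the last observation recorded following the procedure observation carried forward".

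**The concern.** The two parts of the plan do not fit together. If a subject is lost after the 30-day visit and has no later unscheduled mRS, the last post-procedure mRS is the 30-day score. The carried-forward analysis would then let a score from someone who may know the device stand in for an outcome that is defined as blinded.

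This analysis has a particular role among the planned single-value imputations. Baseline imputation (5.4, 8.3.1) uses the pre-stroke mRS, which must be 2 or lower for entry, so every eligible lost subject becomes a success. Worst-score imputation assigns the worst 90-day score seen in the arm. Carrying forward is the only one of the three that draws on the lost subject's own recovery, and it is the one open to unblinded scoring. If assessors who knew the device leaned towards the new one, the error would favour non-inferiority, and agreement with the primary result would reassure less than it appears to.

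**Working it through.** The plan states no figure on this point, so the check is a comparison of text followed by a bound on size.

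**Who scores the 30-day mRS?**

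| Place | 90-day mRS | 30-day mRS |
|---|---|---|
| Visit section (6.8.7, 6.8.6) | Blinded, certified | No assessor named |
| Schedule, footnote 8 (6.8.10) | Yes | No |
| Blinded team's tasks (3.6) | Listed | Not listed |
| List of blinded assessments (3.6.3) | Listed | Not listed |
| Blinded assessor's role (6.4) | Covered | Not covered |

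All five places agree: the visit is unassigned.

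**Which analyses can use the score?**

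- Primary multiple imputation (8.2.2): the listed model variables are six baseline factors, so no.
- Baseline value and worst 90-day score (5.4, 8.3.1): no.
- Tipping-point analysis (8.2.2): not described as using it.
- Last observation carried forward (8.2.2): yes, for subjects lost after day 30 without a later unscheduled mRS.

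**How many subjects?** Section 8.2 expects loss of 5% or less. Arm sizes are 135 (target 270) and 448 / 2 = 224 (maximum ITT).

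- 5% × 135 = 6.75, about 7 per arm.
- 5% × 224 = 11.2, about 11 per arm.

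These are upper bounds. Subjects lost before day 30, or with a later unscheduled score, do not count.

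**How far could the difference move?** Let L be the fraction lost and f the net fraction of those subjects in one arm whose 2-versus-3 call changes because the assessor knows the device. The shift in the carried-forward difference is L × f. The documents give no value for f, so these are assumed:

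- f = 20%: 5% × 20% = 1 point.
- f = 40%: 5% × 40% = 2 points.
- f = 100%: 5 points, the ceiling for one arm.

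Opposite shifts in both arms would double these figures. One changed call is worth 1/135 = 0.74 points at 135 per arm, or 1/224 = 0.45 points at 224.

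For scale, at the planning rates of 46% and 50.5% with 135 per arm, the standard error of the difference is √[(0.46 × 0.54 + 0.505 × 0.495) / 135] = 6.1 points. A shift of 1-2 points is therefore about 0.16 to 0.33 of a standard error, against a margin of 12.5 points.

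**The case against.** The strongest reply is that the plan already means this score to be blinded. Section 3.6.2, which is not tied to any visit, describes assessors as blinded, certified and distinct from the treating physician. The synopsis says the assessing clinical team will be blinded. Section 3.6 describes the blinded team as the one certified in mRS assessment. Section 7.2 has a general sentence on blinded follow-up assessment.

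Much of this stands. A reader might infer that the plan has the treating physician or coordinator score day 30, but the documents do not say so, and Section 3.6.2 points the other way. Still, none of these statements assigns the visit. Section 7.2 concerns the NIHSS, and the specific lists in 3.6 and 3.6.3 leave the 30-day mRS out.

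A second reply is that little depends on it. The 30-day mRS is not a listed endpoint. The carried-forward analysis appears once, in awkward wording, and is missing from the sensitivity analyses named in Sections 5.4 and 8.3.1, which defer details to the SAP. The protocol text does not settle which values may be carried forward. This also stands, and it limits the priority.

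Third, the size rests on a loss ceiling and an assumed shift, and the direction of any leaning is assumed too. The mRS is also scored with a structured form. All of this is accepted, so the figures are bounds and not expectations.

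**Conclusion.** The gap is real but narrow. The 30-day mRS has no assigned assessor, so unblinded scoring is possible though not prescribed. The consequence is limited to the carried-forward sensitivity analysis: at most about 7 subjects per arm at 135, or 11 at 224. Under an assumed net shift of 20-40% in one arm, the movement is at most about 1-2 points, with a one-arm ceiling of 5. This assumes that loss reaches the full 5%, that every lost subject has a day-30 score as the last one, and that the assessor was in fact unblinded.

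A reader might go further and infer that the primary endpoint or the primary non-inferiority test is compromised. The documents do not support that, because the primary multiple imputation is described with baseline factors only. Nor is day 30 the only mRS with loose wording: the unscheduled score is blinded only where possible and also lacks the footnote. The point is a cheap improvement of minor priority.

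**What to change.** 1. In Section 6.8.6, use the wording of Section 6.8.7: "A mRS, assessed by blinded and certified study team member per the RFA-A".
2. In the schedule of events, attach footnote 8 to the 30-day mRS, and reconcile the unscheduled-visit cell with Section 6.8.8.
3. Add the 30-day mRS to Sections 3.6 and 3.6.3 and to the blinded assessor's role in Section 6.4.
4. In Section 8.2.2, state that only blinded mRS scores are carried forward, and say how a lost subject with no such score is handled. The case report form then needs to record whether the assessor was blinded.
5. Give one consistent list of sensitivity analyses in Sections 5.4, 8.2.2 and 8.3.1.

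The cost is protocol wording plus one more short assessment per subject for the blinded team. That team already exists at each site, and Section 6.8.6 allows telemedicine. The change should come before the 30-day scores are collected, because blinding cannot be restored afterwards.

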#### **6.8.7. 90 Day (±15 days) Follow-up**

The 90 Day (±15 days) follow-up visit includes:

- A mRS, assessed by blinded and certified study team member per the RFA-A
- Record any adverse events which occur after the 30 days (±14 days) or discharge time point and up to the time of the 90-day (±15 days) examination.

In-person assessment is preferred, however telemedicine assessment is acceptable if clinical visit not possible.

#### **6.8.8. Unscheduled Visit Follow-up**

The unscheduled visit includes:

- mRS, assessed by blinded and certified study team member per the RFA-A (if possible)
- Concomitant medications
- Record any adverse events which occur since last study visit and up to the time of the 90-day examination.

In-person assessment is preferred, however telemedicine assessment is acceptable if clinical visit not possible.

#### **6.8.9. Completion**

Subjects who successfully complete the 90-day visit will be considered as successfully completing the study.

## 6.8.10. Schedule of Events Summary Table

Study Requirement	Screening	Procedure	Post Procedure				
	Within 24 hrs. of stroke onset	Time 0	24 Hours (-8/+12)	7 Day (-2/+3) or Discharge 	30 Day (±14) 	90 Day (±15) 	Unscheduled
Informed consent	X 						
Pregnancy test	X 						
NIHSS Score	X		X 	X 			
Modified Rankin Scale (mRS)	X 				X	X 	X
Medical history	X						
Physical examination	X			X 			
Blood Pressure and Pulse	X						
Assess/confirm study eligibility	X						
Cerebral Imaging (CT or MRI)	X 		X 				
Hemoglobin and Platelet Count	X 						
Serum Glucose	X 						
Serum Creatinine or eGFR	X 						
INR, aPTT	X 						
Angiography	X 	X 					
Randomization		X					
Mechanical thrombectomy		X					
Concomitant medications	X			X	X	X	X
Record adverse events 	X	X	X	X	X	X	X

(1) Patient or Legally Authorized Representative must sign informed consent prior to screening specific tests which are beyond the local standard of care.

(2) Per institutional standard of care, for females of childbearing potential, subjects must have a documented negative pregnancy test prior to device insertion except in the case of local regulations and ethic committee approvals requiring consent post the emergency situation.

(3) Pre-ictus (Latin for Stroke)

(4) Record all adverse events from the time of signature of the ICF.

(5) To be performed at 7 days (-2/+3 days) or at discharge (whichever occurs first).

(6) Perform baseline to verify the angiographic inclusion/exclusion criteria are met.

(7) Perform angiography after every device pass, and after each additional therapy device pass. Obtain a final angiogram at the end of the interventional procedure.

(8) Assessed by blinded and certified study team member, mRS per the RFA-A.

(9) Visit may be conducted by telemedicine if clinical visit not possible.

(10) Physical exam to be conducted per institution standard of care

(11) If required per local standard of care or inclusion/exclusion criteria

(12) Per institutional standard of care. MRI with DWI is preferred, CT is acceptable. It is preferred that the same imaging modality is used at 24 hour timepoint as at baseline (CT or MRI) to make direct comparison easier.

## 6.9. Imaging Core Laboratory

The objective of the Imaging Core Lab (Core Lab) is to provide an unbiased assessment of the CT, MRI, and angiographic imaging from the study sites. Data provided by the Core Lab will serve as the 'gold standard' and will be used for data analysis. Each angiogram will be read by an experienced Core Lab reader.

The following imaging and angiography variables will be extracted by the Core Lab based on direct prior experience with these measures and scales, using the published definitions and standards:

Pre-Baseline (Outside Hospital, if available):

- ASPECTS
- Hemorrhage

Baseline:

- ASPECTS
- Ischemic core volume – post hoc DWI or CTP rCBF<30% volumes when available
- Tmax > 6 sec volume (if CTP or PWI available)
- Hemorrhage
- Baseline occlusive lesion location
- Presence of occlusions in more than one territory
- CTA collateral score – based on availability (post hoc)

Procedure:

- Presence of stenosis proximal to arterial occlusive lesion
- Arterial occlusive lesion
- Collateral flow grade - ASITN
- eTICI on each device pass
- Distal emboli
- Emboli to new territories
- Evidence of vessel injury

Post-Procedure (24 hour):

- ASPECTS
- Final infarct volume post hoc DWI or CTP rCBF<30% volumes when available
- Hemorrhage (Heidelberg)

Neurological Deterioration or Course Post-Procedure:

- ASPECTS
- Relevant imaging findings and measures, based on availability

The Core Lab will perform an unbiased and blinded assessment of sICH for the primary safety endpoint and hemorrhage related to other safety endpoints. The Core Lab will also have the responsibility to evaluate the 24- hour post-procedure CT/MRI examinations to detect and assess new hemorrhages. Hemorrhages will be radiologically classified as described in Appendix A.

The Core Lab will perform an unbiased and blinded evaluation of the rate of revascularization defined by eTICI scores based on angiographic imaging from the study sites for relevant secondary endpoints.

The Imaging Core Lab is fully compliant with Health Insurance Portability and Accountability Act (HIPAA), the privacy rules and regulations set forth by the U.S. Department of Commerce and the European Commission with regard to the European Data Protection Directive (Directive 95/46/EC), as well as various industry data security standards, such as the Statement on Standards for Attestation Engagements (SSAE 16). Case Report Forms will be completed and provided to the Core Lab, via an electronic data capture system or other designated means.

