#### 3.3. Pre-specified Tertiary (Exploratory) Endpoints

The pre-specified tertiary (exploratory) endpoints of the study will consist of the following. Additional exploratory endpoints may be evaluated.

1. The first exploratory endpoint will be the proportion of subjects with excellent clinical outcome defined as Modified Rankin Score (mRS) of  $\leq 1$  as assessed by a blinded certified assessor at 90 days ( $\pm$  15 days) post treatment.
2. The second exploratory endpoint will be an assessment of reperfusion based on the multinomial eTICI score (as adjudicated by the Core Lab).

3. The third exploratory endpoint will be an assessment of the infarct growth as determined by the change in ASPECTS between baseline and 24 hours (-8/+12 hours) post treatment (as adjudicated by the Core Lab).
4. The fourth exploratory endpoint will be an assessment of the infarct growth as determined by the change in lesion volumes measured by MR/CT perfusion imaging between baseline and 24 hours (-8/+12 hours) post treatment (as adjudicated by the Core Lab, in patient subset with MR/CT perfusion imaging at 24 hours).
5. The fifth exploratory endpoint will be an assessment of final infarct volume at 24 hours (-8/+12 hours) post treatment (as adjudicated by the Core Lab, in patient subset with MR/CT perfusion-weighted imaging at 24 hours).
6. The sixth exploratory endpoint will be an assessment of the time to restoration of flow (i.e., time from arterial puncture to initial restoration of flow; time from arterial puncture to eTICI 2b50 or better, time from first angiogram to initial restoration of flow, time from first angiogram to eTICI 2b50).
7. The seventh exploratory endpoint will be an assessment of Device Technical Success, defined as the proportion of devices with which successful delivery, deployment, and recapture of the randomized device is achieved.
8. The eighth exploratory endpoint will be an assessment of the number of passes to reperfusion of eTICI 2b50.
9. The ninth exploratory endpoint will be an assessment of the number of passes to final result.
10. The tenth exploratory endpoint will be an assessment of the number of passes to achieve reperfusion of eTICI 2b50 or greater (as adjudicated by the Core Lab).
11. The eleventh exploratory endpoint will be an assessment of the proportion of patients who experience embolization of new territory (ENT) (as adjudicated by the Core Lab).

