### 7.1. Cerebral CT or MR Imaging

This study will collect imaging data in line with routine practice as follows:

- Pre-procedure CT/ MRI
- 24-hour (-8/+12) CT/ MRI

All imaging should be in line with standard of care. No extra imaging should be performed for the purpose of the study. No patient should be exposed to extra radiation as a result of participation. It is preferred that the same imaging modality is used at 24 hour timepoint as at baseline (CT or MRI) to make direct comparison easier. MRI DWI is preferred, CT is acceptable.

Any other imaging performed (for example as a result of clinical deterioration) will also be provided.

In the event of abrupt neurologic deterioration or when deemed necessary by the investigator, an emergency CT or an MR imaging evaluation should be performed. An immediate evaluation of the presence/absence of hemorrhage, edema, and/or infarction as contributors to the clinical deterioration will be made. Any imaging taken prior to the routine 24-hour imaging (which may be taken in a time window of 16-36 hours without becoming a protocol deviation) for this reason will be included in the analysis.

Hemorrhages will be classified clinically and radiologically according to the Heidelberg Bleeding Classification (see definitions section for complete description).

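### Section 6.9 accepts a CT perfusion flow threshold as an alternative to DWI for 24-hour infarct volume, so exploratory endpoints 4 and 5 can be understated and confounded with reperfusion in subjects read that way

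*Combined protocol and SAP*

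**What the plan says.** Section 6.9 gives the Core Lab's 24-hour reading rule as "Final infarct volume post hoc DWI or CTP rCBF<30% volumes when available". The baseline ischemic core has the same pair of sources, "post hoc DWI or CTP rCBF<30% volumes when available". No infarct volume from non-contrast CT is listed at either time.

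Section 3.3 defines three relevant exploratory endpoints:

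- Endpoint 3 is "infarct growth as determined by the change in ASPECTS between baseline and 24 hours". It does not depend on perfusion imaging.
- Endpoint 4 is "change in lesion volumes measured by MR/CT perfusion imaging between baseline and 24 hours", in the subset with perfusion imaging at 24 hours.
- Endpoint 5 is final infarct volume, also limited to a subset: "in patient subset with MR/CT perfusion-weighted imaging at 24 hours".

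Section 6.8.4 requires a CT or an MRI at 24 hours. The notes to the schedule of events and Section 7.1 prefer MRI with DWI, accept CT, and prefer but do not require the same modality as at baseline. Section 7.1 also states "No extra imaging should be performed for the purpose of the study". For anterior-circulation strokes, inclusion criterion 6 in Section 6.5 requires CTP or DWI at baseline only in the 6-24 hour window. The synopsis describes the tertiary endpoints as supportive information.

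**The concern.** rCBF<30% describes how much blood is reaching the tissue now. While the vessel is blocked, it can stand in for the infarct core. After a procedure whose purpose is to restore flow, tissue can be dead and yet lie above the threshold. DWI images the lesion itself, so after treatment the two permitted sources no longer measure the same thing.

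The CTP route matters most for subjects who have CT at 24 hours, because rCBF<30% is then the only volume source that Section 6.9 names. Their final volume can be too small, and growth from a CTP baseline can be too small or negative. The error favours whichever arm reperfuses better. Endpoints 4 and 5 are the only volumetric tissue outcomes in the plan and are to be compared between arms. A reading driven partly by reperfusion cannot independently support the reperfusion result.

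The subset is a second problem. Read literally, Section 3.3 leaves out a subject with 24-hour DWI but no perfusion scan and keeps one with CTP alone. Who has perfusion imaging at 24 hours is settled after randomisation by site practice.

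**Working it through.** The plan gives no effect size, standard deviation or power for infarct volume, so there is no planned figure to reproduce. The check compares the texts and then runs a sensitivity calculation.

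**Texts side by side**

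| Item | Section 6.9 | Section 3.3, endpoints 4 and 5 |
|---|---|---|
| Source at 24 h | DWI or CTP rCBF<30% | MR/CT perfusion imaging |
| DWI without perfusion | Readable | Outside the subset |
| CTP without DWI | Readable | Inside the subset |
| Non-contrast CT only | No volume listed | Outside the subset |

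DWI is not perfusion imaging, so the two sections disagree on who is measured and how. Removing DWI-only subjects from the denominator can only raise the CTP share.

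**Inputs**

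- r = 0.74, the planned proportion with eTICI 2b50 or better (Section 8.2, Additional Estimates). In 135 subjects per arm this is 135 × 0.74 = 99.9, about 100.
- c, the share of analysed subjects read by CTP at 24 hours. It is not in the documents, so it is varied from 0 to 1.
- k, the fraction of the true infarct no longer below the threshold in a reperfused, CTP-read subject. It is not in the documents and is set to 0.5 and 1.
- d = 0.121, the non-inferiority margin for the second secondary endpoint (Section 8.3.2), used only as an example of a difference in reperfusion between arms (74% versus 61.9%).

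**Formulas**

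The calculation assumes equal true mean volume whatever the modality or reperfusion status, and correct reading in all other subjects. Then:

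- Relative understatement of mean volume = r × c × k.
- Spurious arm difference when true infarcts are equal, as a share of true mean volume = d × c × k.

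| CTP share c | Understatement, k = 0.5 | Understatement, k = 1 | Spurious difference, k = 0.5 | Spurious difference, k = 1 |
|---|---|---|---|---|
| 0 | 0% | 0% | 0% | 0% |
| 0.25 | 9.25% | 18.5% | 1.5% | 3.0% |
| 0.50 | 18.5% | 37% | 3.0% | 6.05% |
| 0.75 | 27.75% | 55.5% | 4.5% | 9.1% |
| 1 | 37% | 74% | 6.05% | 12.1% |

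For example, with c = 0.5 and k = 1, 0.74 × 0.5 × 1 = 0.37 and 0.121 × 0.5 × 1 = 0.0605.

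**One subject, as illustration**

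Take a 40 cc core on baseline CTP, which is within the 50 cc limit for patients under 80, and suppose the true final infarct is also 40 cc. Recorded final volume is 40 × (1 − k). With k = 0.5 it is 20 cc and growth is −20 cc. With k = 1 it is 0 cc and growth is −40 cc. True growth is 0 cc in both cases.

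**The case against.** The strongest reply is that DWI is named first in Section 6.9 and MRI with DWI is the stated preference. If all 24-hour volumes came from DWI, this mechanism would produce no bias. That is correct. A reader might infer that final infarct volume is always read from perfusion. The text does not say so, and the exposure is limited to the CTP-read share.

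Other points also stand:

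- Infarct growth as a whole is not compromised. Endpoint 3 measures it by ASPECTS on the scans already obtained.
- A reader might infer that growth turns negative in every reperfused subject. Partial reperfusion can leave low-flow tissue, and DWI-to-DWI pairs are untouched. That restored flow confounds a flow threshold is measurement reasoning. The documents do not say how fully rCBF normalises by 24 hours.
- A reader might infer that about three quarters of CTP reads are misleading. The 74% refers to at most three passes, additional therapy may follow (Section 3.5), and eTICI 2b50 means only 50-66% of the territory is reperfused (Appendix A). It is not reperfusion status at 24 hours.
- The subset restriction is disclosed. The documents point to institutional standard of care, which need not differ by arm. They do not show selection by clinical need.
- Section 8.3.2 leaves tertiary analysis details to the SAP. The text available here contains no rule for combining modalities, but that does not show that DWI and CTP values will be pooled without one.
- Replacing CTP with non-contrast CT still leaves two modalities, and a covariate would not make them interchangeable. This is why the fix asks for results by modality.

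None of this removes the permission in Section 6.9 or its mismatch with Section 3.3.

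**Conclusion.** The concern holds in limited form. The plan permits a blood-flow threshold as a 24-hour infarct measure after treatment intended to restore flow, and two exploratory endpoints are worded around perfusion imaging in a way that conflicts with the Core Lab's DWI option. In reperfused, CTP-read subjects, final volume and growth can be understated and confounded with reperfusion.

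The size cannot be fixed from the documents. The 0% to 74% range rests on assumed values of c and k and on equal true volumes. If true infarcts are smaller in reperfused subjects, the understatement for given c and k would be lower. The stronger conclusion, that endpoints 4 and 5 merely restate eTICI, would need a high CTP share and near-complete normalisation, and the documents support neither.

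The consequence is confined to two supportive endpoints. It is worth correcting because the comparison is pre-specified and the correction is cheap.

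**What to change.** Amend Section 6.9, exploratory endpoints 4 and 5 (Section 3.3 and the synopsis) and the Core Lab's reading instructions:

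1. Remove CTP rCBF<30% as a 24-hour infarct measure and keep it for the baseline core only.
2. Define 24-hour infarct volume as the DWI lesion or, where there is no MRI, the non-contrast CT lesion outlined by the Core Lab on the scan already obtained under Section 6.8.4. Give DWI precedence when both exist.
3. Replace the perfusion-imaging subset with all randomised subjects who have that scan.
4. Report volumes by modality.
5. Compute growth only where a baseline DWI or CTP core exists, and show same-modality pairs separately. In practice these are DWI at both times, since a CTP core set against a non-contrast CT lesion is a mixed pair.

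No additional scan is needed, so the limit on imaging in Section 7.1 is respected. The cost is revised wording and extra outlining time. The drawback is that lesion edges on CT at 24 hours are less sharp than on DWI, so the CT volumes will be noisier and should be read alongside the DWI results.
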